10.4.2. Month 12 data

Outcomes to be collected include:

- Graft and patient survival at month 12 post-transplant
- Number of readmissions in past 12 months (and reasons for readmission)
- Presence of transplant-related renal dysfunction
- Healthcare resource use in past 12 months (including inpatient days).
- Lifestyle activity score (see Appendix 6)

The following biochemical outcomes will be recorded at month 12 post-transplant:

- Serum bilirubin (measured in μmol/l)
- Serum alanine transaminase (ALT; measured in IU/L)
- Serum aspartate transaminase (AST; measured in IU/L)
- Serum alkaline phosphatase (ALP; measured in IU/L)
- Blood urea (mmol/L)
- Serum creatinine (μmol/l)

Immunosuppression

Details of maintenance immunosuppression at 12 months post-transplant will be recorded.

11. THE ORGANOX METRA DEVICE

11.1. Device description

11.1.1. OrganOx Limited

OrganOx Limited is a late-stage medical device development company that was founded in April 2008 as a spin-out from the University of Oxford.

11.1.2. The OrganOx metra

The OrganOx *metra* is a normothermic preservation device for use in human liver transplantation. It perfuses the donor liver with blood, oxygen and nutrients, as well as a number of medications, at normal body temperature to replicate physiological conditions and preserve the organ for up to 24 hours. The device provides information as to the haemodynamic, synthetic and metabolic function of the liver during perfusion, which may assist the clinician in assessing the organ's suitability for transplantation.

11.1.3. The OrganOx metra Base Unit

The OrganOx *metra* normothermic perfusion device incorporates a centrifugal pump, an oxygenator, oxygen concentrator, heat exchanger, reservoir, flow probes, pressure sensors, infusions and blood gas analyser together with tubing and connector components. The device is comprised of three main components:

- a reusable base unit which contains software and hardware
- a disposable plastic circuit
- a set of perfusion solutions suitable for 24 hours perfusion

11.1.4. Disposable Set

The disposable set used with the core base unit of the OrganOx *metra* contains all the disposables used with each organ recovery on the *metra* and comprises:

- 1. A disposable tubing set, including a blood reservoir, perfusion lines, a blood oxygenator and centrifugal pump-head together with flow and pressure sensors.
- 2. An organ storage bowl which is pre-connected to the tubing set to contain the organ while on the device.
- 3. Cannulae for the coeliac artery, portal vein and inferior vena cava with easy connection attachment to the perfusion circuit.
- 4. A cannula and connection point for bile collection
- 5. Blood gas sensors for monitoring pO₂, pCO₂ and pH by means of on-line blood gas analysis.

11.1.5. Perfusion Solutions

For the present study all the additives necessary to perfuse and maintain the organ during the storage process, with the exception of sodium taurocholate, are not included in the disposable set provided by OrganOx and will be sourced locally (OrganOx will provide a list of recommended suppliers in the

Clinical Trial Protocol Template version 14.0

CONFIDENTIAL

Instructions for Use (IFU) document). These solutions include bolus injections (given at the start of perfusion) and the maintenance infusions (given throughout perfusion).

The primary perfusion fluid for the liver comprises packed red blood cells, supplemented by colloid solution to normalise the haematocrit and osmolarity— these two components are not included and will be sourced locally.

Before connection of the liver the blood-based perfusate is supplemented with:

- Antibiotic and antifungal agents as per current local protocols. Heparin (anticoagulant) to prevent thrombosis in the circuit. In clinical use, a half-life of ~90 minutes is assumed; on this basis heparin is also given as a maintenance infusion.
- Sodium bicarbonate (buffer) for adjusting the pH of the perfusate.
- Calcium gluconate/calcium chloride to correct the binding of citrate to calcium.

During the perfusion the following are infused at a constant rate:

- Parenteral nutrition solution a source of amino acids and glucose for liver maintenance.
- Insulin to control the perfusate glucose level
- Heparin to maintain anticoagulation.
- A 2% solution of sodium taurocholate in isotonic saline to compensate for loss of bile salts.
- Prostacyclin to optimise micro-perfusion.

The primary fluid for perfusing the organ is packed red cells supplied from blood transfusion centres and supplemented by a commercially-available colloid solution (human albumin solution or Gelofusine as per local protocol) to normalise the haematocrit and osmolarity. Further additions are made to the perfusate to support the liver. All solutions required will be attached to the circuit during set-up and before the liver is attached. The recipient centre will provide the solutions necessary for perfusion with the *metra* including the packed red blood cells. All solutions are prepared immediately before the organ is attached to the device and contain sufficient solution for 24 hours operation, the intended maximum perfusion time for a liver on the device.

11.2. Device Safety

In designing the *metra*, OrganOx has made every attempt to maintain the current practices of organ retrieval and transplant teams, in order to minimise the risk of complications or errors that would prevent a successful retrieval. From a regulatory standpoint, it is important to note that the *metra* is an organ preservation system and its use does not involve direct connection to either the donor or recipient at any time.

The device has been designed according to ISO 13485, the standard that stipulates the requirements for a comprehensive management system for the design and manufacture of medical devices. In addition ISO 14971 specifies a process for a manufacturer to identify the hazards associated with medical devices to estimate and evaluate the associated risks, to control these risks, and to monitor the effectiveness of the controls. As part of the development of the device an extensive risk analysis has been undertaken and the risks identified and minimised in accordance with this standard.

The OrganOx perfusion system is based on the principle that all the perfusion solutions, additives and packed red cells must be removed from the organ prior to transplant. Therefore following the completion of the perfusion, the perfusion solution is flushed out of the organ with HTK solution. OrganOx has deliberately designed the operation of the device such that it will require minimal changes to current transplant clinical practice.

11.3. Regulatory Aspects

The OrganOx metra has been used in over 800 clinical liver perfusions worldwide. It has been tested in a multicentre Phase III clinical trial demonstrating both safety and efficacy.

The Organox device is CE marked and will be used within its approved indication. Therefore this is not a regulatory device trial. There are no current plans for the manufacturer to use clinical data from the study to support a change to CE marking of the product.

11.4. Device and Disposables Accountability

All participating centres have access to an OrganOx metra device that is also available for general clinical use. Disposable sets will be provided for the study by OrganOx and should only be used for the preservation of livers recruited into this study. Any livers being perfused outside of the current study should use the hospitals own supply of disposable sets.

Device accountability will be undertaken at each local site throughout the study for the reusable unit(s) and disposable sets (sterilisation/assembly batch number and disposable set number). The manufacturer and lot number for each perfusion solution will also be recorded on the case report forms (CRFs). The site will maintain a log of usage of both the retained unit, disposable set and perfusion solutions used throughout the study recording the lot number used against each subject (on the CRF).

At the end of each procedure the OrganOx *metra*, and any unused disposable and perfusion solutions will be disposed of on site. Details of total numbers of disposable sets provided for trial use will be recorded.

11.5. Device Maintenance

Device cleaning and routine maintenance will be the responsibility of the local transplant centre storing the device. Full details for cleaning and routine maintenance required will be provided in the instructions for use (IFU), and appropriate training will be provided as part of the device training described in section 15.3.

If a device develops a fault during the study, it will be removed from service and a replacement loan device provided as soon as practically possible to allow continuation of recruitment.

12. SAFETY REPORTING

The below sections describe the required reporting for adverse events within the clinical trial. This is in addition to the standard incident reporting to the device manufacturer and to Clinical Governance at NHSBT. It is a statutory condition of a licence for procurement or transplantation activity to rapidly report to NHSBT (acting on behalf of the HTA), relevant and necessary information concerning adverse events which may influence the quality and safety of organs. All study sites will therefore follow their usual procedures for highlighting concerns – by completing an NHSBT incident submission form:

https://safe.nhsbt.nhs.uk/IncidentSubmission/Pages/IncidentSubmissionForm.aspx

These reports will be reviewed periodically by the Data Monitoring Committee (DMC).

Untoward incidents related to the process of organ retrieval and transplantation are routinely collected by NHSBT. Further detail may be found here:

https://www.odt.nhs.uk/odt-structures-and-standards/governance-and-quality/tell-us-about-an-incident/

12.1. Adverse Event Definitions

Adverse Event (AE)	Any untoward medical occurrence, unintended disease or injury, or untoward clinical signs (including abnormal laboratory findings) whether or not related to the study intervention.					
Serious Adverse Event (SAE)	 Led to death Resulted in serious deterioration in the health of the subject that: resulted in a life-threatening illness or injury resulted in persistent or significant disability or incapacity required in-patient care or prolongation of hospitalisation resulted in medical or surgical intervention to prevent life-threatening illness or injury or permanent impairment to a body structure or a body function resulted in congenital anomaly or birth defect These are handled under the SAE reporting system. Planned hospitalisation for a pre-existing condition, or a procedure required by the trial protocol, without serious deterioration in health, is not considered a serious adverse event. 					

Severity definitions

The following definitions will be used to determine the severity rating for all adverse events:

Mild: awareness of signs or symptoms, that does not interfere with the subject's usual activity or is transient that resolved without treatment and with no sequelae.

Moderate: a sign or symptom, which interferes with the subject's usual activity.

Severe: incapacity with inability to do work or perform usual activities.

NB: to avoid confusion or misunderstanding of the difference between the terms "serious" and "severe", the following note of clarification is provided: "Severe" is often used to describe intensity of a specific event, which may be of relatively minor medical significance. "Seriousness" is the regulatory definition supplied above.

12.2. Anticipated Serious Adverse Events

Liver transplantation is a life-saving procedure but is associated with serious life-threatening complications which would be expected during the study and which we do not propose to report as SAEs, except those reported as outcomes:

- Primary non function: 0.8% in DBD, 4.0% in DCD livers
- Early allograft dysfunction (Olthoff definition): 25% DBD, 40% DCD
- Hepatic artery thrombosis: 4-15%, depending whether anomalous arterial supply required reconstruction or not
- Post reperfusion syndrome: 30%, more common in DCD than DBD
- Biliary anastomotic breakdown in 10%, more common in DCD
- Post operative haemorrhage requiring reoperation: 10%
- Acute rejection: 20%
- Acute kidney injury: 25% in DBD, 50% in DCD
- Chest complications: sepsis; effusion; paralysed right hemidiaphragm: common
- Ascites: universal if pre-existing ascites, common if not pre-existing
- Line sepsis
- Biliary anastomotic stricture: 10%
- Ischaemic cholangiopathy: 4% DBD, 20-25% DCD
- Retransplantation in first year: around 11% for DBD, rising to 17% for DCD
- Graft failure or sepsis
- Hospitalisation for pre-existing condition that has not deteriorated.

The investigator will exercise their medical judgment in deciding whether an abnormal laboratory finding or other abnormal assessment is clinically significant. However, if in the opinion of the investigator, the frequency or severity of the event is greater than would be expected then it must be reported.

12.3. Assessment of Causality

The relationship of each adverse event to the trial procedures, conduct or intervention must be determined by a medically qualified individual according to the following definitions:

Related: The adverse event follows a reasonable temporal sequence from the trial procedures. It cannot reasonably be attributed to any other cause.

Not Related: The adverse event is probably produced by the participant's clinical state or by other modes of therapy administered to the participant.

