12.4. Procedures for Reporting Serious Adverse Events

It is the responsibility of the local investigator to ensure that all adverse events which fall in to the category of Serious Adverse Events (SAEs) are reported to NHSBT Clinical Trials Unit, Chief Investigator, central investigators and, if required, to their local R&D department as soon as possible after becoming aware of the event but no later than 24 hours. AE not meeting the definition for serious will not be collected.

Data will include but not be limited to:

- A description of the event
- The dates of the onset and resolution
- Action taken
- Outcome
- Assessment of relatedness to the trial procedures, conduct or intervention
- How the event qualifies as serious
- Expectedness

The severity of events will be assessed on the following scale: 1 = mild, 2 = moderate, 3 = severe.

Adverse events that occur during the course of the study should be treated by established standards of care that will protect the life and health of the study subjects.

Serious adverse events will be collected from transplant until 12 months following the transplant, via a purposely designed MACRO database (access via www.ctu.nhsbt.nhs.uk/macro). SAEs will be automatically notified to NHSBT CTU. If the eCRF is unavailable for any reason, a paper version of the form should be completed, scanned and emailed to serious adverse [contact]. Within the following 5 working days, the local investigator may be required to provide additional information on the SAE in the form of a written narrative. This should include a copy of the completed SAE form, and any other diagnostic or relevant information that will assist the understanding of the event.

Additional and further requested information (follow-up or corrections to the original case) should also be added to eCRF using a new SAE Report Form. NHSBT CTU will ensure that all SAEs are reported to the Sponsor .

The clinical reviewers will review the SAEs and, if they feel they pose an immediate risk to patient health or safety, then they will report them to the DMC immediately, and the REC within 15 calendar days of the Chief Investigator becoming aware of the event. This includes any SAEs that the local investigator assesses to be unexpected and related to the study procedure.

Clinical Trial Protocol Template version 14.0

CONFIDENTIAL

© Copyright: The University of Oxford and Oxford University Hospitals NHS Foundation Trust 2018

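### The two causality categories in section 12.3 leave a gap, and Related is drawn too strictly and too narrowly for the expedited reporting that depends on it

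*Protocol*

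**What the plan says.** Protocol section 12.3 opens by requiring a causality decision on every event: "The relationship of each adverse event to the trial procedures, conduct or intervention must be determined by a medically qualified individual". It then offers two answers only.

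- The first is "Related: The adverse event follows a reasonable temporal sequence from the trial procedures. It cannot reasonably be attributed to any other cause".
- The second is "Not Related: The adverse event is probably produced by the participant's clinical state or by other modes of therapy administered to the participant".

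Section 12.4 makes relatedness a required item of each SAE report, again against procedures, conduct and intervention. It also sets the expedited route. Clinical reviewers look at the SAEs and, "if they feel they pose an immediate risk to patient health or safety, then they will report them to the DMC immediately", with the REC informed within 15 calendar days of the Chief Investigator becoming aware. The next sentence adds a class that is always in: "This includes any SAEs that the local investigator assesses to be unexpected and related to the study procedure".

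Section 12.2 lists 16 kinds of complication "which would be expected during the study and which we do not propose to report as SAEs, except those reported as outcomes". Many carry a background rate, for example "Primary non function: 0.8% in DBD, 4.0% in DCD livers". An override applies to the list: "if in the opinion of the investigator, the frequency or severity of the event is greater than would be expected then it must be reported".

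**The concern.** A two-way classification has to give every event a place. This one sets a high bar on both sides: Related needs every other reasonable cause to be excluded, and Not Related needs another cause to be probable. Between them lies the event with two credible explanations.

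That middle ground matters in this trial. Every eligible liver has a DUI above 0.27, the recipients are ill, and the operation itself carries serious risks. For most SAEs some cause other than NMP will be reasonable, whether or not NMP played a part.

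Two things are at stake. Investigators must record an answer that the definitions do not supply, so sites will resolve the gap differently and the recorded relatedness will not be comparable. In addition, the only class of SAE that is expedited by rule depends on this definition.

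**Working it through.** No sample size, error rate or event count enters this point, so there is nothing to compute. The check is to sort the possible cases by the two definitions and then follow them into section 12.4.

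**Step 1. Sort the cases under section 12.3.**

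| Link to NMP | Other cause | Meets Related? | Meets Not Related? |
|---|---|---|---|
| Plausible | None reasonable | Yes | No |
| Plausible | Plausible, not probable | No | No |
| Plausible | Probable | No | Yes |
| None in time | Probable | No | Yes |
| None in time | None probable | No | No |

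Two of the five rows have no category. The second is the important one. The third shows that an event to which NMP contributed is Not Related whenever something else is the probable cause. Only the first row yields Related, and there NMP is the sole reasonable explanation. A contributory role therefore never qualifies.

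**Step 2. Compare the scope.** The opening of 12.3 and the SAE data items in 12.4 cover procedures, conduct and intervention. The Related definition covers trial procedures only. The expedited class in 12.4 covers the study procedure only. Three scopes are in use for one decision.

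**Step 3. Follow the cases into section 12.4.** There are two triggers.

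- Trigger A is the reviewers' view that there is an immediate risk. It needs no finding on relatedness, and it has no stated criteria.
- Trigger B is unexpected and related. It needs both parts.

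For an event on the 12.2 list, trigger B fails on expectedness under any causality wording. For an SAE not on the list, expectedness is no bar and the Related definition decides. That is where the wording has its effect.

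**Step 4. An illustration from the protocol's own terms.** Portal vein thrombosis is a safety outcome in sections 6.2 and 9.8 but is not on the 12.2 list. The disposable set in section 11.1.4 includes a portal vein cannula. Suppose an investigator thinks that cannulation may have contributed and that the implant operation may have too, neither being probable. This is row two: neither category applies and trigger B does not fire, although a possible contribution from the intervention is what a causality assessment should record. The suspicion is hypothetical; the protocol does not state such a risk.

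**The case against.** Four counter-arguments have force.

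- **A reader might infer that the expedited route cannot trigger at all.** The protocol does not support that. Trigger A stays open for any reported SAE, and an event with no other reasonable cause, such as a clear device failure, can still be Related.
- **A reader might infer that an excess of primary non-function or another listed graft event would go unreported because of this definition.** It would not be because of this definition. Those events are expected under 12.2, so they miss trigger B however Related is worded, and expected counts from the listed rates do not measure this defect. The main graft events are also collected as outcomes regardless of cause, and the 12.2 override covers severity as well as frequency.
- **A reader might infer that the trial report would falsely reassure.** Section 13.2 summarises safety outcomes by classification and severity, not by relatedness, and graft failure and death within 12 months enter the primary endpoint. A low count of related SAEs could still be misread, but it is not the planned safety summary.
- **Oversight is broader than 12.3.** SAEs reach the CTU and Chief Investigator within 24 hours, and the DMC reviews accumulating data and NHSBT incident reports. A DMC charter exists and is not shown, so the lack of a pooled table of listed events in the protocol is no finding.

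All four limit the consequence. None closes the gap between the two definitions, restores the missing scope, or gives trigger A any criteria.

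**Conclusion.** Section 12.3 is wrong as written: the categories are not exhaustive, contribution cannot count, and the scope of Related is narrower than the assessment the section asks for. The effect is confined to two places: how relatedness is recorded for SAEs with more than one credible cause, and which SAEs outside the 12.2 list must be expedited by rule rather than at the reviewers' discretion.

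The gap and the scope mismatch follow from the text alone. That trigger B will rarely apply is an inference from the strict wording and from the many competing causes in these recipients. The protocol gives no number for it, and none is offered here. The conclusion about listed events assumes that an event on the 12.2 list counts as expected; the protocol does not say whether one reported under the override is then treated as unexpected.

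**What to change.** In section 12.3, define Related as a reasonable possibility that the trial procedures, conduct or intervention caused or contributed to the event. Define Not Related as the complement: no reasonable possibility. Use the same scope in the expedited sentence of section 12.4, and carry the wording to the SAE form. Whether a decision to transplant that was prompted by NMP should count as a cause is debatable, since it rests on a counterfactual that nobody observes; the repair does not depend on it.

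The cost is a protocol and form amendment, and somewhat more SAEs classed as related and needing review. Timing adds to it. Recruitment was planned to end on 11/10/2023, SAEs are collected for 12 months after transplant, and the latest listed version is dated 23/07/2024, so many SAEs may already be classified. Those should be reassessed under the new definition with the site's existing entry kept, so that the SAE data are not split between two definitions.
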